#### 6.8.4.2. Subjects with CGM data

For subjects with CGM-data, the following properties will be analyzed

- Fraction of measurements in the following ranges
  - < 54 mg/dL
  - $\geq 54$  mg/dL and < 70 mg/dL
  - $\geq 70$  mg/dL and  $\leq 180$  mg/dL
  - > 180 mg/dL and < 250 mg/dL
  - > 250 mg/DL
- Additionally, the fraction of measurements in the following ranges will be tabulated for each treatment group.
  - < 70 mg/dL
  - $\geq 70$  mg/dL and < 140 mg/dL
  - > 140 mg/dL
- Glycemic variability will be analyzed and the following statistics will be tabulated
  - standard deviation (SD)
  - coefficient of variation (CV),

#### 6.8.5. Insulin Dosing

Insulin dosing information will be tabulated by treatment and visit. The information extracted from the eCRF and that taken from device uploads (only available for pump users) will be tabulated separately.

Data extracted from the pumps will be limited to two weeks (14 days) prior each visit in order to guarantee a stable status.

Descriptive statistics for the following properties will be tabulated.

- Average basal insulin dose
- Average bolus insulin dose
- Average daily bolus count

For each of these three properties, the changes between doses respectively counts reported as pre study values and those at a given visit will be reported both absolute and relative.

### 6.9. Therapy Parameters

The following event frequencies will be listed for each individual subject and will also be tabulated by treatment group and visit. Additionally, event frequency differences between V4 and V5 will be tabulated. Tabulations will be performed both based on the number of affected subjects and on the total wear time of the three study devices during the analyzed period.

- Hyperglycemia and related events (e.g., Ketosis or Ketoacidosis) likely caused by insulin underdosing
- Hypoglycemia
- Hospitalizations

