### 4.2 Secondary Objectives

The secondary objectives of this study are to evaluate:

- Psychological parameters that describe or affect therapy:
  - Diabetes-related Emotional Distress assessed by PAID-5.
  - Device satisfaction
  - Device and Treatment Preference
- Physical parameters that describe therapy changes or success:
  - HbA1c
  - Change in weight and BMI
  - glycemic variability
- Therapy parameters that describe therapy changes or may affect the results
  - Indication for commencement of CSII
  - Type of insulin used
  - Total daily insulin dose (TDD)
  - Total daily basal insulin dose (TBD)
  - Average number of SMBGs per day
  - Frequency of hypoglycemic events
  - Frequency of hyperglycemia
  - Frequency of consultations between scheduled visits, emergency and call center calls, hospitalizations and absenteeism from work/school
- Device specific parameters that may affect user acceptance
  - number of pods/ infusion assemblies falling off prematurely
  - average infusion assembly usage time
  - number, type and intensity of skin reactions
- Parameters that may affect socio-economic acceptance
  - Insulin amount left in device at reservoir change / device discard

CONFIDENTIAL

- Amount of waste, inferred by total material consumption

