### **9.2.4 Hyperglycemic Episode**

Hyperglycemia is defined as high blood glucose readings, a recommended threshold to intervene could be defined as values above 250 mg/dL (13.9 mmol/L). However, investigators should consider the condition of the individual subject.

Only hyperglycemia episodes in combination with medical intervention or additional diagnostic procedures have to be documented as AE in the eCRF, as described in Section 9.3.1.1.

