#### 9.3.1 Expected Adverse Events

##### 9.3.1.1 Captured Expected Adverse Events

The following expected AEs may occur at any time in the course of managing diabetes. Immediate or short-term risks to subjects from some of these expected AEs are higher than those identified under Non-Captured Expected AEs.

Therefore, for the purposes of this study, the following expected AEs will be considered captured expected AEs and the AE Form in the eCRF needs to be completed:

- Symptomatic hypoglycemia episodes (see Section 9.2.2).

- Hyperglycemia in combination with medical intervention.
- Hyperglycemia in combination with medical intervention or suspected by the site staff to be caused by insulin leakage or infusion set occlusion.
- Infusion site infection and abscesses, if applicable.
- Unintentional needle stick injury with the guiding needle of the infusion set, if applicable.
- Plaster reactions to the infusion set, if applicable.
- Generalized hypersensitivity reactions.
- Ketosis and ketoacidosis.

These captured expected AEs will be handled as follows:

Subjects will be instructed to follow their personal physicians' instructions for management of low and high blood glucose values or otherwise as instructed by the Investigator.

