### **9.3.1.2 Non-Captured Expected Adverse Events**

Non-Captured expected AEs may occur at any time in the normal course of managing diabetes. For the purpose of this study, they will be considered as non-captured expected AEs and will not be documented in the eCRF, these include:

- Asymptomatic hypoglycemia episode (see Section 9.2.1).
- Hyperglycemia without medical intervention.
- Hyperglycemia with a suspected cause other than infusion set leakage or occlusion and without medical intervention.
- In the event of a sore finger, subjects will be advised to avoid taking self-monitoring blood glucose samples from that finger.
- In the event of a mild infection at a lancing site, the study subject will be reminded to wash hands before all blood tests and encouraged to consult their nurse or physician on the management of an infection.
- Minor skin damage due to plaster removal which disappears within a few hours.
- Minor bleeding into the infusion set plaster or into the catheter or tubing, if applicable.
- Mild discomfort by plaster or cannula that may result into replacement decision by the subject.
- Also, both planned ambulant contacts and planned hospitalizations for training purposes will be considered non-captured adverse events.

Since these non-captured expected Adverse Events identified above are common as well as expected and pose minimal immediate risk to the subjects, they will not be tracked and logged as AEs during the course of the study. Investigators may log reports of these non-captured expected AEs as is customary within their practice.

These non-captured expected AEs will be handled as follows:

Subjects will be instructed to follow their personal physicians' instructions for management of low and high blood glucose values as well as for minor skin damage, minor bleeding and mild discomfort.

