## 2.2. Study Design

This study is conducted as a prospective, multinational, multicenter, three-arm study where adults with type 1 diabetes will be enrolled in approximately 20 sites.

A total of 180 subjects will be randomly allocated in a 1:1:1 ratio to the three treatment groups.

Due to the character of the used devices, no blinding procedure will be utilized.

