### 3.5.5. Coding of Adverse Events and Medical History

Adverse event and medical history terms are coded using the Medical Dictionary for Regulatory Activities (MedDRA) terminology version in effect at the time the database is closed. MedDRA term level (LLT, PT, and SOC) are utilized depending on the particular needs of a given analysis. What term level will be used will be defined with the analysis definition.

Certain medical conditions, e.g. hyperglycaemia and ketonuria have completely different MedDRA codings, however they may be caused by identical reasons, e.g., lack of insulin. Medical Safety may therefore request pooling of such events. If this is applied, it will be explained as part of the respective analysis.

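### SAP 6.9 does not tabulate the protocol's hyperglycaemia frequency: as worded, it pools in ketosis and ketoacidosis and restricts by a presumed cause with no stated rule

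*SAP*

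**What the plan says.** Protocol 4.2 lists "Frequency of hyperglycemia" among the secondary therapy parameters. Protocol 11.6 and SAP 2.1 repeat the item. None of the three places attaches a cause or joins it to another event.

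SAP 6.9, the section that sets out the event-frequency tables, has this item instead: "Hyperglycemia and related events (e.g., Ketosis or Ketoacidosis) likely caused by insulin underdosing". The other two items there, hypoglycaemia and hospitalisations, have no qualifier. The tables are by treatment group and visit, with differences between Visits 4 and 5, and are based both on affected subjects and on device wear time.

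SAP 3.5.5 gives background. It notes that hyperglycaemia and ketonuria are coded far apart in MedDRA although "they may be caused by identical reasons, e.g., lack of insulin", and adds: "Medical Safety may therefore request pooling of such events". Any pooling is to be explained where it is used.

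On blinding, SAP 2.2 says: "Due to the character of the used devices, no blinding procedure will be utilized".

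**The concern.** The SAP row differs from the protocol parameter in two ways. It is wider, because ketosis, ketoacidosis and an open-ended set of related events come in. It is narrower, because on its plain wording an event must probably result from too little insulin. A reader who looks in the SAP for the protocol's parameter will take the 6.9 row as the answer, and it is not the same quantity.

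The restriction could also act unequally across arms. Protocol 9.3.1.1 names leakage and infusion-set occlusion as suspected causes of hyperglycaemia, and these belong to pump delivery. A judgement about under-delivery, made without written criteria while the treatment is known, may keep a different share of events on a pump than on injections. The same applies within arm B, where 6.9 tabulates the change from Visit 4 (MDI) to Visit 5 (Solo).

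**Working it through.** The plan gives no event rate or expected count for this parameter, so there is no figure to reproduce. The check compares the passages.

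1. **Parameter against table row.** Protocol 4.2, Protocol 11.6 and SAP 2.1: hyperglycaemia, any cause, on its own. SAP 6.9: hyperglycaemia plus related events, with a cause phrase. The SAP therefore also disagrees with itself (2.1 against 6.9), and no reason for the change is given.

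2. **Can the 6.9 rule be applied as written?** It would need three things:
   - A term list for the related events. 6.9 gives only examples.
   - A criterion for the presumed cause. None is given. The causality categories in Protocol 9.4, and the causality summaries in Protocol 11.7 and SAP 6.12, concern the relation to the device, not underdosing.
   - A named assessor. None is given. SAP 3.5.5 names Medical Safety, but only for an optional request to pool.

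   By contrast, SAP 3.5.4.1 handles a different attribution problem (safety events on the day of Visit 4) by saying whose assignment is used and what the default is.

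3. **When is the event set fixed?** SAP 2.11 and 6.5 plan an analysis once all subjects have passed Visit 4 or withdrawn. Neither 3.5.5 nor 6.9 requires the terms or the rule to be settled before those tables are produced.

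4. **What reaches the AE form?** Protocol 9.3.1.1 captures "Hyperglycemia in combination with medical intervention or suspected by the site staff to be caused by insulin leakage or infusion set occlusion". Protocol 9.3.1.2 leaves out "Hyperglycemia with a suspected cause other than infusion set leakage or occlusion and without medical intervention". Protocol 9.2.4 is worded differently again: "Only hyperglycemia episodes in combination with medical intervention or additional diagnostic procedures have to be documented as AE in the eCRF". Without medical intervention, capture under 9.3.1 thus already turns partly on suspected leakage or occlusion. The 6.9 phrase adds a second cause condition to the first.

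5. **What a second filter could do.** If a share s of captured events is kept in each arm, then

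   ratio of tabulated rates = ratio of captured rates × (s in Solo ÷ s in MDI).

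   The documents give no shares. Purely assumed values show that the direction is open: 0.7 ÷ 0.5 = 1.4; 0.8 ÷ 0.4 = 2.0; 0.4 ÷ 0.8 = 0.5. With equal shares the factor is 1. These values are not estimates, and 6.9 plans no rate ratio; the formula only describes how two tabulated rates would compare.

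6. **What else is reported?** SAP 6.12 tabulates AEs by system organ class and preferred term, with events, affected subjects, percentages and rates per year of device use, and no cause filter. It also counts diabetic ketoacidosis separately. SAP 6.8.4 tabulates the share of glucose readings in fixed bands, including above 180 and above 250 mg/dL.

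**The case against.** Four arguments weigh against the point.

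- **The phrase may not be a filter.** Read with SAP 3.5.5, the words on underdosing may only explain why differently coded terms are grouped. On that reading no hyperglycaemia is dropped and step 5 falls away. This is possible, but it is not what 6.9 says on its face. Pooling would still separate the row from the protocol parameter, and two programmers could count different events from the same sentence.
- **The unfiltered counts exist elsewhere.** This stands and limits the harm. It does not close the gap: nothing marks the 6.12 tables as the protocol's parameter, the 6.8.4 tables give shares of readings rather than event frequency, and the ketoacidosis count omits ketosis alone.
- **An all-cause row is not free of cause either.** This also stands, because of Protocol 9.3.1. The change removes only the condition added by the SAP.
- **The item is minor.** It is descriptive and lies outside the hierarchical tests. SAP 6.1 rules out testing unless it is explicitly specified, and 6.9 specifies none.

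A reader might also infer that no form records the cause, or that the sponsor's safety function decides which events count. The documents support neither. The eCRF is not among them, and Protocol 9.3.1.1 does ask site staff about one insulin-delivery cause. SAP 3.5.5 gives Medical Safety an optional, disclosed right to request pooling; it says nothing about who judges cause.

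**Conclusion.** The point holds in a limited form. The 6.9 row, as worded, is not the parameter listed in Protocol 4.2, Protocol 11.6 and SAP 2.1, and its cause condition cannot be applied consistently because no field, criterion, assessor or term list is described. In an unblinded trial the share of events kept could differ between the pump and MDI arms. Neither the direction nor the size can be estimated from the documents, so it would go too far to say that the Solo-MDI comparison is biased by any given factor, or that the protocol's parameter goes unreported altogether.

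The consequence is confined to one descriptive secondary row. The primary DTQ analysis is unaffected. The conclusion on filtering assumes that the cause phrase restricts which events count; if it only describes the grouping, the pooling and the missing term list remain as the defect.

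**What to change.** In SAP 6.9, replace the item with two rows:

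- *Hyperglycemia: all events captured on the AE form, regardless of presumed cause*
- *Ketosis and ketoacidosis*

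Show any pooled or cause-restricted set only as a supplementary table. Fix its preferred terms and its rule before by-arm tables are seen. If the Visit 4 interim has already run, fix them before database closure and state that timing.

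Add a footnote to the hyperglycaemia row: without medical intervention, AE capture depends on suspected leakage or occlusion (Protocol 9.3.1.1 and 9.3.1.2), so the count is not fully cause-free and should be read beside the 6.8.4 glucose-range tables.

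The cost is SAP wording, one extra row and a footnote; no new data are needed. The downside is that the all-cause count includes episodes unrelated to insulin delivery.

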### 6.10. Diabetes Associated and Not Diabetes related Diseases

Both diabetes associated and non-diabetes related diseases will be listed by subject.

### 6.11. Additional analyses

It will be tested, whether there is a bias in the fraction of subjects withdrawing from the different treatment arms using the Fisher test.

### 6.12. Evaluation of Safety Variables

The safety analysis will be based on the SP and on the device, a subject is using at the time, when a safety event occurs. Since all subjects in treatment arms B and C will receive an Accu-Chek® Solo micropump system at Visit 4 (week 26) and will use it until the end of the study, AEs and SAEs occurring at or after Visit 4 will be attributed to the Accu-Chek® Solo micropump

system. Distinction will be handled and documented according to the description in section 6.2.1.

All AEs will be coded using the Medical Dictionary for Regulatory Activities (MedDRA). Summaries of incidence rates of overall AEs and of individual AEs by MedDRA system Organ Class and Preferred Term will be prepared. Furthermore, summaries will be tabulated for all AEs, AEs by maximum severity, AEs by strongest causality to study device.

Summaries will include number of events, number of subjects affected, the percentages of all subjects for a given treatment, and the events per year of use for a given device.

Defective devices will be tabulated and listed by device type and treatment arm.

Deaths, SAEs and AEs leading to withdrawal will be listed separately.

Episodes (numbers) of the following AEs will be summarized:

- Symptomatic hypoglycemia
- Severe hypoglycemia (SAEs)
- Diabetic Ketoacidosis (SAEs)

The following ADEs are of particular interest:

- ADEs leading to replacement of device.

Incidence rates of all ADEs and of these ADEs and AEs of special interest (as captured on the AE Form in the eCRF) per 100 patient years will be calculated together with exact two-sided 95% CIs assuming that the number of special AEs observed in the study is Poisson distributed.

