## 2.10. Populations for Analysis

Due to the design of the study with a parallel phase between visits 1 and 4 and a one-armed phase in which all subjects will use the Accu-Chek® Solo micropump system, analysis will distinguish between these phases. Wherever appropriate, the treatment arm, to which a subject is randomized, will be denoted as “arm”, the current treatment as “trt” in listings and tables. E.g., a subject randomized to treatment arm B (MDI) will therefore have the analysis assignments B for both, arm and trt between visits 1 and 4, while the corresponding assignments will be B as arm and A as trt between visits 4 and 5.

The following populations are defined for analysis:

- The safety population (SP) is defined as all enrolled patients with data documented at at least one of the visits 1 to 5.
- The full analysis population (FAS) will follow the intention to treat principle, i.e., all subjects will be analyzed according to the treatment arm they are randomized to..
- The per-protocol (PP) population will be defined on a per visit basis. For a given visit, it will include all subjects that will have completed this visit and have no severe protocol deviations.

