### 3.5.3. Incomplete Dates

For a limited number of fields, the eCRF allows to enter incomplete dates in cases if the exact date is not known to the subject or the investigator, e.g., the date when diabetes was first diagnosed. For analysis, dates where only the year is known/given, July 1 will be used. If the month but not the day is known, 15 will be inserted as day. E.g., “2005” will be replaced by “01-Jul-2005” and “Sep-2010” will be replaced by “15-Sep-2010.

### 3.5.4. Special Handling of Visit 4

#### 3.5.4.1. Safety Events at Visit 4

Subjects randomized to treatment arm B (MDI) and C (OmniPod) will receive the Accu-Chek® Solo micropump system only at Visit 4. As a consequence, safety events (AEs and SAEs) cannot be assigned to either the randomized treatment or the Accu-Chek® Solo micropump system based on the date of the event alone. If an assignment to a device will be available from the investigator and confirmed by Safety, it will be used for the analysis. Otherwise, the event will be assigned to the Accu-Chek® Solo micropump system to guarantee conservative results.

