#### 3.5.4.2. Device Use Time

Subjects will receive their study device (Accu-Chek® Solo micropump system, MDI, or OmniPod®) at Visit 2. Additionally, as described above, study subjects randomized to arms B and C will utilize two devices at the day of Visit 4. Consequently, for all analyses utilizing the number of days a given device is used, use time will be calculated starting at Visit 2. For subjects randomized to treatment arms B (MDI) and C (OmniPod), the day of Visit 4 will be counted for

both, that is for the randomized device and for the Accu-Chek® Solo micropump system. For subjects in treatment group A, the Visit 4 day will however only be counted once.

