### 6.2. Analysis Populations

Primary population for all except safety relevant analyses is the FAS as described in section 2.10. Additionally, for completeness, the primary analysis will also be performed on the per protocol population. All safety relevant analyses will be performed on the SP.

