#### 6.2.1. Distinction of Study Phases

As already described in 2.10, the study consists of two phases. To allow for easy distinction e.g., in listings, two variables, Arm and Trt are assigned to data acquired from each subject depending on the study phase and device assignment during data assessment.

| Arm Variable | Phase 1 (V1 - V4) |              | Phase 2 (V4 – V5) |              |
|--------------|-------------------|--------------|-------------------|--------------|
|              | Device            | Trt Variable | Device            | Trt Variable |
| A            | Solo              | A            | Solo              | A            |
| B            | MDI               | B            | Solo              | A            |
| C            | OmniPod           | C            | Solo              | A            |

Descriptive statistics for V5 data will both be calculated separately for each study arm and overall for all subjects.

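### Adverse-event percentages for Solo pool 39-week and 13-week users beside 26 weeks of MDI or OmniPod, and no Solo column limited to the randomised phase is specified

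*SAP*

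**What the plan says.** SAP 6.12 assigns each adverse event to the device in use when it occurred. For arms B and C, "AEs and SAEs occurring at or after Visit 4 will be attributed to the" Solo system. Each summary gives the number of events and the "number of subjects affected, the percentages of all subjects for a given treatment, and the events per year of use for a given device". SAP 6.3 sets the percentage denominator as all patients in the population or group.

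For the separation of phases, 6.12 points to 6.2.1, where "two variables, Arm and Trt are assigned to data acquired from each subject depending on the study phase and device assignment during data assessment". In that table Trt = A covers arm A in both phases and arms B and C in phase 2. On use time, SAP 3.5.4.2 adds: "For subjects in treatment group A, the Visit 4 day will however only be counted once". That fits Solo time summed across the two phases.

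Some text points the other way. SAP 2.10 says "analysis will distinguish between these phases", and 6.2.1 says "Descriptive statistics for V5 data will both be calculated separately for each study arm and overall for all subjects". SAP 6.9 tabulates hyperglycemia-related events, hypoglycemia and hospitalizations by treatment group and visit, and 6.8.1.4 does so for insertion sites. Neither 6.12 nor Protocol 11.7 specifies an adverse-event column for arm A between Visit 2 and Visit 4.

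For events on the day of Visit 4 in arms B and C, SAP 3.5.4.1 has its own rule: "If an assignment to a device will be available from the investigator and confirmed by Safety, it will be used for the analysis". Failing that, Solo is the default.

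**The concern.** The percentage of subjects with at least one event depends on how long each subject was observed. The MDI and OmniPod columns are parallel-phase data from randomised arms, with 26 planned weeks each. The Solo column, on the natural reading, contains one randomised arm followed for 39 weeks and two switched arms followed for 13 weeks. Those two contribute only subjects who reached Visit 4, and arm C enters with 26 weeks of pump use. The three percentages are therefore neither equal in exposure nor a randomised contrast.

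A reader comparing the columns could take an artefact of follow-up for a difference between devices, and at the planned allocation the artefact favours the investigational device. The design does offer a randomised safety comparison with equal planned exposure, but the plan does not specify its Solo column for the system organ class and preferred term, severity or causality tables.

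The border between the phases is also unclear. On the day of Visit 4, 3.5.4.1 allows an event to stay with MDI or OmniPod, while 6.12 sends it to Solo.

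**Working it through.** **Inputs.** Durations of 39, 26 + 13 and 26 + 13 weeks (SAP 2.4); 180 subjects at 1:1:1 (SAP 2.2); drop-out of up to 18% (SAP 2.8). The documents give no adverse-event rate, so constant rates of 0.1 to 4 per year, equal on all devices, are assumed.

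**The plan's own figure.** The plan states no adverse-event percentage or exposure. Its 60 per arm reproduces: a two-sample t-test for a difference of 20, SD 30, two-sided 0.05 and 90% power gives 48.26, rounded up to 49; 49/0.82 = 59.8, rounded up to 60.

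**Planned exposure, full retention.**
- Solo: (60×39 + 120×13)/52 = 75 patient-years in 180 subjects, mean 21.7 weeks.
- MDI and OmniPod: 60×26/52 = 30 patient-years each, 26 weeks per subject.

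**Percentage affected.** p(t) = 1 − exp(−rate × t), t in years. Solo = [60·p(0.75) + 120·p(0.25)]/180; comparator = p(0.5). At 1 per year: (60×0.528 + 120×0.221)/180 = 32.3%, against 39.3%.

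| Rate per year | Solo % | Comparator % | Gap (points) | Ratio |
|---|---|---|---|---|
| 0.1 | 4.1 | 4.9 | 0.8 | 0.83 |
| 0.25 | 9.7 | 11.8 | 2.0 | 0.83 |
| 0.5 | 18.3 | 22.1 | 3.9 | 0.83 |
| 1 | 32.3 | 39.3 | 7.0 | 0.82 |
| 2 | 52.1 | 63.2 | 11.1 | 0.83 |
| 4 | 73.8 | 86.5 | 12.7 | 0.85 |

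**Source of the gap.** If every Solo user had the mean 21.7 weeks, the Solo percentage at 1 per year would be 34.1%. From unrounded values, the 39/13-week mix accounts for 1.7 of the 7.0 points (25%) and shorter mean exposure for the rest. The mix accounts for 3% at 0.1 per year and for 58% at 4 per year (7.3 of 12.7 points).

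**Other allocations.** Protocol 2.1 allows no randomisation to group C where OmniPod is not on the market, so arm C could be smaller. Assumed splits, full retention:
- 70/70/40: mean 23.1 weeks, ratio 0.86-0.89.
- 80/80/20: mean 24.6 weeks, ratio 0.89-0.94.
- 90/90/0: mean 26.0 weeks, ratio 0.91-0.99.

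**Drop-out.** Assume 11 of 60 per arm leave uniformly over weeks 0-26. The Solo denominator becomes 60 + 98 = 158, with 64.0 patient-years. The ratio is 0.87-0.90 at 60/60/60. With the same drop-out proportion it is 0.90-0.94 at 70/70/40 and 0.95-1.04 at 90/90/0, where the deficit can vanish or reverse.

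**Rate per year.** With constant rates the Solo-to-OmniPod ratio is 1.00. Suppose instead that rates double in the first 2 weeks on a pump (base 1 per week). OmniPod has 28/26 = 1.077. Solo has (41 + 15 + 13)/65 = 1.062 if arm C does not restart the early period at the switch (ratio 0.99), or (41 + 15 + 15)/65 = 1.092 if it does (ratio 1.01). If rates double for the first 13 weeks on each new device, the rates are 1.6 and 1.5 times the later rate, a ratio of 1.07.

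**Visit 4 day.** 1/183 = 0.5% of MDI or OmniPod exposure; the share of events is larger if findings at the visit are dated to that day.

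**After the change.** Arm A in Visit 2 to Visit 4 has 60×26/52 = 30 patient-years, as do MDI and OmniPod. With equal rates all three columns agree (22.1% at 0.5 per year, 39.3% at 1).

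**The case against.** The strongest reply is that the pooled layout is inferred. No table shell is given, 6.12 refers to a section on distinguishing the phases, and 2.10 says arm and trt will be shown in tables as well as listings. A programmer could split by phase. That is correct, but the text makes the split possible without requiring it. The V5-by-arm sentence concerns Visit 5, not the parallel phase.

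Second, the same summaries give events per year of use, and ADEs and events of special interest get rates per 100 patient-years with exact intervals. This stands and limits the problem to the percentages, which are printed in the same tables.

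Third, 6.9 and 6.8.1.4 already split several key outcomes by visit. This also stands; the gap is in the general system organ class and preferred term, severity and causality tables. The repeat on other populations in 6.13.2 does not clearly fill it, because under 6.2 "All safety relevant analyses will be performed on the SP".

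Fourth, for rare events the gap is small against sampling error: 0.8 points at 0.1 per year, with a standard error of about 3.1, and 7.0 points at 1 per year, with a standard error of about 7.1. True, but the shift is systematic, runs in the same direction in every row at 60/60/60, and can be avoided.

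Fifth, summaries by device have a basis in Protocol 11.7, and total Solo experience is worth reporting. Agreed; the pooled table should stay. On Visit 4, 3.5.4.1 can be read as the specific rule that refines 6.12, but the SAP does not say so.

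**Conclusion.** The concern holds. On the natural reading of 6.12 with 6.2.1, the percentage columns compare unequal exposure and do not form a randomised contrast, and the plan does not specify the Solo column that would. With identical devices, constant rates of 0.1-4 per year, 60 per arm and full retention, Solo would show 0.82-0.85 times the comparator percentage; with 18% drop-out, 0.87-0.90. The artefact shrinks if arm C is smaller, and with no arm C plus drop-out it could run either way.

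These sizes rest on assumed event rates and an inferred table layout. Exposure-adjusted rates are unaffected under constant rates and moved by 1% to 7% in the start-up scenarios tried. The tables are descriptive, Protocol 2.2 says safety is not a primary endpoint, and no hypothesis test changes. This is a worthwhile, inexpensive improvement in safety reporting, not a threat to the trial's main conclusion.

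**What to change.** In SAP 6.12:

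- Add adverse-event tables for Visit 2 to Visit 4 by randomised arm, with events, number and percentage of subjects, and rate with exact 95% CI. Name these as the between-device comparison.
- Show Solo events from Visit 4 to Visit 5 separately by arm.
- Keep the pooled Solo table as total Solo exposure, based on rates. Either omit its percentages or footnote that exposure is unequal and not randomised. The footnote sits better with Protocol 11.7, which asks for percentages.
- Reconcile 3.5.4.1 and 6.12 on events dated to the day of Visit 4, so that each event falls in one phase by one rule.

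The cost is one more table set from the existing Arm and Trt variables, plus SAP wording. The Solo interval is wider in the randomised comparison. At an assumed 1 event per patient-year, 30 events in 30 patient-years give an exact 95% CI of 67.5-142.8 per 100 patient-years, against 78.7-125.4 for 75 events in 75. The pooled table still supplies the narrower interval for total Solo use.
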